The CONCERN Early Warning System:

Study Protocol and Analysis Plan

NCT03911687

INVESTIGATORS

[name], RN and [name], RN

PROTOCOL TITLE

Communicating Narrative Concerns Entered by RNs (CONCERN): Clinical Decision Support Communication for Risky Patient States

FUNDING NINR

R01NR016941

VERSION DATE

November 11, 2016:

Table of Contents

Content	Pages
I. Original Study Protocol and Statistical Analysis Plan (submitted to/funded by NINR and IRB approved)	2-4

1. Original Study Protocol and Analysis Plan

Aim 3 below is focused on the CONCERN Early Warning Score Trial Design and Analysis Plan and is excerpted from R01 grant funded in 2017 (NINR 1R01NR016941, COmmunicating Narrative Concerns Entered by RNs (CONCERN): Clinical Decision Support Communication for Risky Patient States). Protocol below was IRB approved November 2016.

Aim 3. Evaluate the impact of the CONCERN SMARTapp notification system on patient outcomes, for the primary outcomes of in-hospital mortality and length of stay (LOS) and secondary outcomes of cardiac arrest, unanticipated transfers to the intensive care unit, and 30-day hospital readmission rates.

Table 1. Sample and Setting Calendar Year 2014 (all adult patients)

Site	Beds	Occupancy Rate	In-patient Mortality	30-day Readmit	CONCERN implementation processes
PHS-BWH	777	95%	1001	18%	
PHS-NWH	300	94%	312	10%	
NYP-CUMC	745	95%	1261	18%	
NYP-Allen	300	75%	98	10%	will use open source tools, APIs (application program interfaces), web services, and SMART tools developed at Harvard Medical School. The

need for site specific, local EHR configurations will be minimized using this approach. Our technology solution will allow for continuous refinement of algorithm, pushing out a new version every 3 months to provide consistent amount of time to evaluate and track outcomes for each version.

CONCERN Intervention Trial Design will be a multiple time-series intervention (see Table 2). Please also refer to Table 1 for study sites and samples. Baseline data will be collected at all study sites. Silent release mode (no SMARTapp notification) will be used in non-equivalent control units and as a post-intervention unit control to evaluate if notifying clinicians can decrease rates of length of stay on non-ICU units and rates of 30-day hospital readmissions. In Table 2 the different versions indicate dynamic, adaptive functionality. The adaptive function utilizes [name] inpatient acuity calculation¹¹⁸ to determine if the pattern of nursing documentation has changed. We have built in time for a "burn-in" phase to evaluate adoption and adaptation to our algorithm.

Table 2. Trial Design with Multiple Time-series Intervention

Study Arm	Site	Pre-intervention (6 months)	Phase 1 (3 months) [burn-in phase]	Phase 2a (3 months)	Phase 2b (3 months)	Phase 3 (3 months)
Control Groups	Site A	B	XX	V1 silent	V2 silent	V3 silent
	Site B	B		V1 silent	V2 silent	V3 silent
	Site A	B		V1 active	V2 active	V3 active
	Site B	B		V1 active	V2 active	V3 active

B = baseline data; none = no intervention; silent = CONCERN App will function but will not display to clinician, active = CONCERN App will display to clinician. V1=version 1; V2=version 2 refined based on continuous monitoring of data

CONCERN intervention trial data collection and analysis includes collection of pre and post-intervention data during the 6 months before the intervention and 12 months after the intervention (see **Error! Reference source not found.** for timeline). Prior to conducting hypotheses tests, descriptive statistics will be used to describe outcome variables and key confounding variables. We propose a generalized linear mixed model to examine the impact of the CONCERN system on each of the two primary outcomes: in-hospital mortality and length of stay. This model is used to deal with combined data from multiple sites and can account for changes over time. This model allows different baselines and trajectories for different ICUs and non-ICU settings and can include both patient level and unit level covariates. We will also use a generalized linear mixed model for an interrupted time series analysis for unit level analysis. We will include a variable for closed versus open units in our analysis. We estimated statistical power for the comparison of mortality rates between the intervention and non-intervention periods and between silent and active model periods. All power calculations were based on 2-sided tests with alpha = 0.05. Using hospital patients' statistics, we expected at least 2,000 total admissions per month (ranging from 38 to 270 admissions in different units) with a mean mortality rates of 37.5 deaths per 10,000 inpatient days (ranging from 11.9 to 48.8), see Table 1. Using a very conservative number of total 50,000 inpatient days in each intervention period, we will have at least 80% statistical power to detect a difference of less than 1% relative difference in mortality rates. Because the 1% change in mortality are smaller than a clinically meaningful difference, we should have sufficient sample size. When examined by different campuses, using a very conservative value of inpatient days in one campus of 6000 inpatient days in each intervention period, we will have at least 80% statistical power to detect a difference of less than 2% relative difference in mortality rates. There is no consensus regarding the best method for analyzing length of stay. Length of stay has been analyzed using both Poisson models (or NB, or other related models such as Zero-truncated Poisson models) and survival models (such as Cox PH models).¹¹⁹ Both approaches will be applied to length of stay and the better performing model will be retained. We will use the logit link function for 30-day hospitalization outcomes. We will calculate the Number Needed to Treat during the months when the CONCERN system is on silent mode and in active mode for the non-ICU versus ICU and at each site for the

prevention of each of the following outcomes: length of stay, and 30-day hospital readmission rates. Additional secondary outcomes include 30-day hospital readmission, cardiac arrest, and unanticipated transfers to the ICU as well as analytics of CONCERN system log-files for clinician usage metrics. The following statistical tests will assess evaluate the reliability and validity of the results and effects of the CONCERN intervention: mutual information, association statistics including t-test and regression analysis, sub-sampling, and cross-validation and control of confounders (e.g., patient acuity with Charlson's Comorbidity Index, [name] inpatient acuity calculation¹¹⁸, and other validated acuity tools).^{3,45,57}

References from Original Protocol and Statistical Analysis Plan (NINR 1R01NR016941)

57. Goodwin L. Data mining issues and opportunities for building nursing knowledge. *J Biomed Inform*. 2003;36(4-5):379-388. doi:10.1016/j.jbi.2003.09.020.

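### Two primary outcomes have no success rule or multiplicity control, and the length-of-stay model is to be chosen on an undefined criterion

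*Combined protocol and SAP*

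**What the plan says.** Aim 3 lists in-hospital mortality and LOS together as primary. The paragraph on data collection and analysis then proposes a generalized linear mixed model for "each of the two primary outcomes: in-hospital mortality and length of stay". Nowhere does the plan rank the two, divide alpha between them, name a multiplicity method, or say whether one or both must be significant.

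One significance level appears: "All power calculations were based on 2-sided tests with alpha = 0.05". The sentence before it sets its scope: "We estimated statistical power for the comparison of mortality rates between the intervention and non-intervention periods and between silent and active model periods". No testing level is given for LOS.

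On LOS, the plan remarks that the best method is not agreed, names count models (Poisson, negative binomial, zero-truncated Poisson) and survival models (Cox), and continues: "Both approaches will be applied to length of stay and the better performing model will be retained". It does not define performance or say on which data it will be judged. A further mixed model, for a unit-level interrupted time series, is added without an explicit rank against the first model.

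**The concern.** There are two separate gaps.

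- **Success rule.** With two primary outcomes and no rule, a significant result on one alone could be reported as a primary success. The 5% level used for power would then not be the error rate of the trial's main conclusion.
- **LOS model.** Count and survival models answer different questions: a ratio of mean stays against a hazard ratio for discharge. Choosing between them on the trial data leaves both the test and the estimand open until results exist. If the choice is influenced by the estimated effect, it also adds to the error rate.

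**Working it through.** The plan states no overall type I error, so there is no figure of its own to reproduce. The steps below assume one test per primary outcome at two-sided 0.05 (critical value 1.96), which extends the level in the power statement to both outcomes. They count one comparison per outcome, although the power sentence names two.

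**1. Either outcome suffices, one LOS model.**
- Independent tests: 1 − 0.95² = 0.0975, or 1.95 × 0.05.
- Any dependence: at most 0.05 + 0.05 = 0.10.
- Correlated tests: 1 − P(|Z₁| ≤ 1.96 and |Z₂| ≤ 1.96), with (Z₁, Z₂) bivariate normal. The plan gives no correlation, so a range is shown:

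| Correlation, mortality and LOS tests | Familywise error |
|---|---|
| 0 | 0.0975 |
| 0.3 | 0.095 |
| 0.5 | 0.091 |
| 0.8 | 0.078 |

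**2. Both outcomes required.** A false claim needs a rejection of at least one true null at 0.05 together with a rejection of the other, so its probability does not exceed 0.05.

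**3. Either outcome suffices, and the LOS model with the smaller p-value is kept.** This was simulated with two million draws of three correlated normal test statistics (mortality, LOS count model, LOS survival model). The correlation between the two LOS tests is an assumption:

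| Correlation of the two LOS tests | Error for LOS alone | Overall, mortality independent | Overall, mortality–LOS correlation 0.5 |
|---|---|---|---|
| 0.95 | 0.065 | 0.11 | 0.103 |
| 0.8 | 0.078 | 0.124 | 0.115 |
| 0.5 | 0.091 | 0.136 | 0.125 |

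The overall range is roughly 0.10 to 0.14. For comparison, three independent tests give 1 − 0.95³ = 0.143.

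**4. The LOS model is kept on a fit criterion blind to the intervention effect.** Selection then adds little, and the step 1 figures stand.

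**5. Price of testing first at 0.025.**
- On the log scale, detectable effects grow by (2.24 + 0.84)/(1.96 + 0.84) = 3.08/2.80 = 1.10.
- As an illustration for mortality, take the plan's 37.5 deaths per 10,000 inpatient days and 50,000 days per period. The rate agrees with Table 1: 2,672 deaths over 712,808 bed-days (beds × occupancy × 365) is 37.5 per 10,000. A two-proportion calculation that ignores clustering puts the relative reduction detectable with 80% power at 26.9% for alpha 0.05 and 29.4% for alpha 0.025. Power at the 26.9% effect falls from 80% to 71%.
- The 26.9% does not match the plan's statement of 80% power for a relative difference below 1%, which was not reproduced. That is a separate matter; the figure serves here only to price the change.

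**The case against.** A reader might infer that the trial tests each outcome at 0.05, keeps whichever LOS result looks better, and so runs at about twice its stated alpha. The documents do not support that as a statement of fact.

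- **The level.** The 0.05 is tied to power calculations for mortality. Its use for each primary test is an inference, though no other level is offered.
- **The rule.** The plan says neither either nor both. Under a both-outcomes rule there is no inflation.
- **Independence.** Death in hospital ends the stay, so the two outcomes are linked and 0.0975 is towards the high end. Even at correlation 0.8, however, the error is 0.078.
- **The source of the doubling.** It comes from having two outcomes. The LOS model choice is a separate addition.
- **The selection.** The LOS sentence follows a citation of a comparison of LOS modelling strategies, and the plan elsewhere lists sub-sampling and cross-validation. Choice by fit or prediction is at least as natural a reading as choice by p-value.
- **The time series.** The mixed model comes first and the time series is introduced as an addition, which suggests an order without stating it.

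These points make the figures conditional. They do not supply the missing success rule, the missing selection criterion or a fixed LOS estimand.

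**Conclusion.** The point holds in conditional form. The plan has two primary outcomes with no success rule and no multiplicity control. If either suffices at 0.05, the familywise error is up to about 0.10; if both are required, it is no more than 0.05. The undefined LOS choice adds almost nothing if blind to the intervention effect. It takes the overall error to roughly 0.10 to 0.14 if made on p-values, given the assumed correlations.

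The open LOS estimand does not depend on any of these assumptions. A Cox model is also not, in its usual form, the generalized linear mixed model that the plan first proposes for both outcomes, so the primary LOS analysis is not settled within the plan's own text.

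**What to change.** 1. State whether success requires one primary outcome or both. If both, no alpha split is needed. If either, use Holm: the smaller p-value at 0.025 and, if that passes, the other at 0.05. This keeps the familywise error at or below 0.05 under any dependence.
2. Name the mixed model with patient-level data as the primary analysis and the unit-level interrupted time series as supportive.
3. Fix one LOS model, and with it the estimand, before outcomes are compared between silent and active modes. Alternatively, choose it by a stated measure of fit on the six-month pre-intervention data only. Report the other model as a sensitivity analysis. The deadline is set by that comparison because the documents describe no blind, and the active application is visible to clinicians.

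The cost is plan wording and no new data. The downside under Holm is that an outcome tested at 0.025 needs an effect about 10% larger on the log scale; if the other outcome has already passed, it is tested at 0.05 and loses nothing. A model chosen on baseline data may fit later data less well, which the sensitivity analysis would show.

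### No sentence makes the active-versus-silent difference in change from baseline the treatment effect, and power is given only for a before-after contrast and an unadjusted silent-active contrast

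*Combined protocol and SAP*

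**What the plan says.** **Design (Aim 3, trial design paragraph and Table 2).** The design is a multiple time series with six months of baseline at all sites. On the controls it says: "Silent release mode (no SMARTapp notification) will be used in non-equivalent control units and as a post-intervention unit control". As printed, Table 2 gives every row a baseline. It then runs two rows silent and two rows active, at Sites A and B, through the same Phases 2a, 2b and 3. The active rows carry no arm label in this copy, so the table is read with some caution.

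**Models (Aim 3, data collection and analysis paragraph).** A generalized linear mixed model (GLMM) is proposed for in-hospital mortality and length of stay (LOS). The GLMM is said to handle several sites and may include time. On how settings may differ, the plan says: "This model allows different baselines and trajectories for different ICUs and non-ICU settings". Covariates at patient and at unit level may be entered. A second analysis is then named: "We will also use a generalized linear mixed model for an interrupted time series analysis for unit level analysis".

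**Contrasts.** The power sentences concern mortality only and cover the "comparison of mortality rates between the intervention and non-intervention periods and between silent and active model periods". Separately, the plan will calculate the "Number Needed to Treat during the months when the CONCERN system is on silent mode and in active mode", for LOS and readmission only.

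**The concern.** The design collects what a controlled estimate needs: baseline and follow-up in both silent and active units. The analysis text does not say that the estimate will use all four of these cells.

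At least four different quantities fit the wording: a before-after term, a post-period active-versus-silent term, a level or slope change in an interrupted time series without a control series, and an active-versus-silent by baseline-versus-post term. They answer different questions and could disagree, even in sign. If the choice is left until the data are seen, any of them could be reported as the primary result. The two for which power was stated are the two most open to bias: calendar change for the first, and pre-existing differences between units for the second.

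**Working it through.** **1. The contrasts side by side**

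| Contrast | Concurrent control? | Stated use of baseline in both arms? | Power given? |
|---|---|---|---|
| Intervention vs non-intervention periods | No | No | Yes, mortality |
| Silent vs active | Yes, under Table 2 | No | Yes, mortality |
| Number needed to treat by mode | Yes, under Table 2 | No | No |
| Active vs silent, change from baseline | Yes | Would use it | Not named, no power |

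**2. The plan's own inputs and power figure**

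- Rate: beds × occupancy × 365 in Table 1 sums to about 712,808 bed-days. Deaths are 1001 + 312 + 1261 + 98 = 2,672. The rate is 2,672/712,808 = 37.5 per 10,000 days, as stated.
- Expected deaths per period: the plan takes "Using a very conservative number of total 50,000 inpatient days in each intervention period", so 50,000 × 37.5/10,000 = 187.5.
- Power for a 1% relative difference between two such periods: the standard error of the log rate ratio is sqrt(1/187.5 + 1/(187.5 × 0.99)) = 0.1035, and −ln 0.99 = 0.01005. The ratio is 0.097, so power is about 3% in the right direction.
- The stated 80% is therefore not reproduced as a relative difference. It would hold if 1% meant an absolute difference. That is a separate matter and does not decide this point.

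**3. Detectable reduction at 80% power, two-sided 0.05, Poisson, no clustering**

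The multiplier is 1.960 + 0.842 = 2.802, and r is the rate ratio to be detected.

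- Two cells, 187.5 deaths each at the null: −ln r = 2.802 × sqrt(1/187.5 + 1/(187.5r)). r = 0.730, a 27% reduction.
- Four cells, 50,000 days each: −ln r = 2.802 × sqrt(3/187.5 + 1/(187.5r)). r = 0.646, a 35% reduction.
- Four cells, 50,000 days per period split between arms (93.75 deaths per cell): r = 0.527, a 47% reduction.
- 50,000 days per three-month phase and per arm, six baseline months against nine (Phases 2a to 3): 375 and 562.5 deaths per arm. −ln r = 2.802 × sqrt(2/375 + 1/562.5 + 1/(562.5r)). r = 0.762, a 24% reduction.
- The same, with each phase's 50,000 days split between arms (187.5 and 281.25 deaths): r = 0.676, a 32% reduction.

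At equal cell size, a true 27% reduction that the two-cell contrast detects with 80% power is detected by the four-cell term with 54%: −ln 0.73 / sqrt(3/187.5 + 1/(187.5 × 0.73)) = 0.315/0.153 = 2.06, less 1.96.

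**4. Clustering (illustration)**

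Unit-by-period variation adds 4s²/k to the variance, with k units per arm and s the unit-by-period SD on the log scale. The documents give neither. With an assumed k = 10 and s = 0.10 to 0.15, the 35% becomes 38% to 40%. If s is left out of the model, simulation puts the false-positive rate of the four-cell test at 7% to 10%.

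**5. Crude before-after testing (illustration)**

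Assume no true effect, 187.5 deaths at baseline and a secular fall d. The test statistic has mean |ln(1−d)| / sqrt(1/187.5 + 1/(187.5(1−d))). For d = 5%, 10% and 15% this is 0.49, 0.99 and 1.51, giving rejection rates of 8%, 17% and 33%. The falls are assumed. No matching figure is given for silent versus active, because the documents report no difference between silent and active units. None is given for LOS, because they report no LOS mean or variance.

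**The case against.** **Both named contrasts might be called uncontrolled.** The documents do not support that for silent versus active. Table 2 runs the two concurrently, and the text names the silent units as controls. The weakness of that contrast is non-equivalence without stated baseline adjustment.

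**A reader might infer that the plan will test crude contrasts.** It does not say so. The proposed analyses are a GLMM, which may include time and covariates, and a unit-level interrupted time series; the closing analysis sentence adds control for acuity and comorbidity. The 8%, 17% and 33% rejection rates therefore describe crude before-after testing under assumed falls, not the GLMM.

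**The model may already handle unit differences.** The sentence on baselines and trajectories can be read as giving each ICU and each non-ICU unit its own terms, which would absorb at least part of the pre-existing difference. That reading is fair. But letting units differ does not say which coefficient is the treatment effect. The model text says what the model can do and does not commit to an effect term.

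**Some remedies are preference.** This also stands in part. A controlled interrupted time series is an acceptable form of the primary analysis. The handling of burn-in is for the investigators to settle, particularly as the Phase 1 cells are hard to read in this copy.

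**Conclusion.** The point holds in this form: the plan describes a controlled design but does not name a controlled treatment effect, and it gives power only for a before-after mortality contrast without a concurrent control and a concurrent silent-active contrast without stated baseline adjustment. This should be fixed, with medium confidence. The conclusion rests on the text and not on any simulated error rate.

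The range of 24% to 47% for the controlled term assumes Poisson deaths at 37.5 per 10,000 days and no clustering. Its width comes from two things the plan leaves open: whether a period is a three-month phase, and whether its 50,000 days are per arm or in total. On every reading the stated 80% power for a relative difference below 1% does not carry over to the controlled term.

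**What to change.** 1. For mortality and for LOS, state that the primary treatment effect is the active-versus-silent by baseline-versus-post term in the GLMM, or the equivalent arm-specific change in a controlled interrupted time series. Include unit and unit-by-period random effects and calendar time.
2. Treat crude before-after and silent-active comparisons, including the number needed to treat by mode, as descriptive. Keep version-specific effects (V1, V2, V3) as secondary.
3. State whether burn-in data enter the estimate, the same way in both arms. The 12 post-intervention months in the text match Table 2's four three-month phases only if Phase 1 is counted.
4. Replace the power statement with one for this term, giving days per arm and period, the number of units, and an assumed range for unit-by-period variation.
5. Reconcile the post-intervention unit control and the wording about silent and active months with Table 2. Both suggest silent time within the same unit, which the table as printed does not show.

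**Cost.** Wording and a new power calculation; no new data. Precision is lower than for the simple contrasts (about 35% against 27% at 50,000 days per cell, more with clustering). The term also relies on parallel trends, which six baseline months can check only weakly.

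### In-hospital mortality, a primary outcome, has no stated link or denominator, and the only scale given and powered (deaths per inpatient day) rises when co-primary length of stay falls; fix admissions as the denominator before analysis

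*Combined protocol and SAP*

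**What the plan says.** All of the relevant text is in Section 1 (Aim 3) of the combined protocol and SAP.

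- **Outcomes.** In-hospital mortality and LOS are both primary. The trial design paragraph asks whether notifying clinicians lowers LOS on non-ICU units.
- **Mortality scale.** The data collection and analysis paragraph gives a planning figure of "mean mortality rates of 37.5 deaths per 10,000 inpatient days". The power statement ("We estimated statistical power for the comparison of mortality rates between the intervention and non-intervention periods") rests on 50,000 inpatient days per period, and the campus version again counts days: "using a very conservative value of inpatient days in one campus of 6000 inpatient days in each intervention period".
- **Models.** A generalized linear mixed model is proposed for both primary outcomes. It "can include both patient level and unit level covariates", and "This model allows different baselines and trajectories for different ICUs and non-ICU settings". There is a second model: "We will also use a generalized linear mixed model for an interrupted time series analysis for unit level analysis". Neither is given a distribution, link, offset or denominator for mortality.
- **Other outcomes.** The same paragraph does name a link elsewhere ("We will use the logit link function for 30-day hospitalization outcomes") and lists candidate models for LOS.
- **Admissions.** The only counts are in one sentence: "we expected at least 2,000 total admissions per month (ranging from 38 to 270 admissions in different units"). Table 1 lists beds, occupancy and deaths but no admissions, and no risk of death per admission is stated or powered.

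**The concern.** Inpatient days equal admissions times mean LOS. A mortality rate per inpatient day therefore has the other primary outcome in its denominator. If alerts shorten stays and the risk of death per admission does not change, the same deaths are divided by fewer days and the rate goes up. Silent control units do not cancel this, because the fall in LOS is expected where the app is active.

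Two things are at stake. If the powered scale is used, the mortality contrast is pushed against the intervention precisely when it succeeds on LOS: a real benefit can be hidden, or harm suggested where there is none. If the scale simply stays open, the denominator of a primary outcome can be chosen after the data are seen.

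**Working it through.** **1. Reproduce the plan's rate (Table 1).** Bed-days = beds × occupancy × 365.

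| Site, in Table 1 order | Bed-days | Deaths | Per 10,000 days |
|---|---|---|---|
| 1 | 777 × 0.95 × 365 = 269,425 | 1,001 | 37.15 |
| 2 | 300 × 0.94 × 365 = 102,930 | 312 | 30.31 |
| 3 | 745 × 0.95 × 365 = 258,329 | 1,261 | 48.81 |
| 4 | 300 × 0.75 × 365 = 82,125 | 98 | 11.93 |
| All | 712,809 | 2,672 | 37.49 |

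This matches the stated 37.5 (11.9 to 48.8), so the powered denominator is bed-days. Expected deaths per period: 50,000 × 37.5/10,000 = 187.5.

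**2. Effect of LOS on the per-day rate.** Let r be the cut in risk per admission and f the cut in mean LOS. Rate ratio = (1 − r)/(1 − f). If only non-ICU units are affected and they hold a share s of days, the pooled ratio at r = 0 is 1/(1 − s·f). The plan gives no expected LOS effect and no s; the values of f and s = 0.7 are assumptions.

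| LOS cut | Affected non-ICU unit | Pooled, s = 0.7 |
|---|---|---|
| 5% | 1/0.95 = 1.053 | 1/0.965 = 1.036 |
| 10% | 1/0.90 = 1.111 | 1/0.93 = 1.075 |
| 15% | 1/0.85 = 1.176 | 1/0.895 = 1.117 |

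Within an affected unit, a 10% fall in both risk and LOS gives 0.90/0.90 = 1.00: the benefit disappears.

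**3. Illustrative error rates, pooled ratios, no true effect (r = 0).** P(significant increase) = Φ(ln RR/SE − 1.96); nominal value 2.5%. Deaths are Poisson, with 187.5 in each cell.

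- Two periods: SE = √(2/187.5) = 0.103.
- Active and silent units, before and after (four cells): SE = √(4/187.5) = 0.146.
- The four-cell design with variance doubled for clustering (assumed): SE = √(8/187.5) = 0.207.

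| LOS cut | ln RR | Two periods | With silent controls | Variance doubled |
|---|---|---|---|---|
| 5% | 0.0356 | 0.053 | 0.043 | 0.037 |
| 10% | 0.0726 | 0.104 | 0.072 | 0.054 |
| 15% | 0.1109 | 0.188 | 0.115 | 0.077 |

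**4. Illustrative loss of power, pooled, 10% LOS cut.**

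- Two periods, r = 0.27 (the effect with 80% power in this set-up, not a plan figure): SE = √(1/187.5 + 1/(187.5 × 0.73)) = 0.112. Apparent ratio 0.73/0.93 = 0.785. Power falls from 80% to 58%.
- With silent controls, r = 0.354 (80% power here): SE = √(3/187.5 + 1/(187.5 × 0.646)) = 0.156. Apparent ratio 0.646/0.93 = 0.695. Power falls from 80% to 65%.

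**5. Sensitivity.**

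- A model with separate ICU and non-ICU baselines weights a common effect roughly by deaths. With an assumed 50% of deaths on non-ICU units, a 10% LOS cut gives exp(0.5 × 0.1054) = 1.054, and the three set-ups give 7%, 5.5% and 4.4%.
- With more deaths the problem grows. At Table 1's hospital-wide volume, 2,672/4 = 668 deaths per quarter, SE = √(2/668) = 0.0547, and the pooled two-period figure at a 10% cut is Φ(0.0726/0.0547 − 1.96) = 0.26.
- The planning inputs may not describe the study units: 712,809 days / (12 × 2,000 admissions) = 29.7 days per admission, so the two figures probably cover different populations.

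**6. Power on the per-admission scale.** Assume mean LOS of 5 to 8.33 days (8.33 = 50,000 days / 6,000 admissions). Admissions n = 50,000/LOS = 10,000 to 6,000; risk p = 0.00375 × LOS = 1.88% to 3.12%. A log-odds test, each cell adding 1/(n·p(1 − p)) to the variance, has power 0.806 to 0.810 (two periods, r = 0.27) and 0.807 to 0.810 (with controls, r = 0.354), whatever f is. The per-day figure is 0.80 with LOS unchanged.

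**The case against.** The strongest reply is that the bias is hypothetical. Deaths per inpatient day appear only in the power text. The outcome is called in-hospital mortality, the model admits patient-level covariates, and Charlson adjustment is planned; all of that suits a per-admission binary model at least as well. This stands. A reader might infer that the plan commits to a per-day mortality analysis, or that the trial's mortality result will be biased. The documents support neither. Per-day use is most plausible in the unit-level time series, but that is a judgement, since the plan does not say which outcomes the series covers.

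A reader might also apply the full factor 1/(1 − f) to all 187.5 deaths and report a 7%, 17% and 35% chance of an apparent increase in two periods. That does not fit the plan's stated target of LOS on non-ICU units. The full factor belongs to an affected unit's own series, which would not carry 187.5 deaths. The illustrations also use equal cells, whereas Table 2 has a 6-month baseline and 3-month phases.

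Finally, death per admission is not neutral either. Earlier discharge can move deaths outside the hospital, which would favour the intervention, and unit-level admissions require transfers to be attributed when ICU transfer is itself an outcome. Deaths per day is a legitimate rate with a different meaning. These points limit the remedy and must be stated openly. They do not justify leaving the denominator of a primary outcome unset.

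**Conclusion.** The point holds as a conditional one. It is certain that mortality has no stated link, offset or denominator, and that the only scale stated and powered is per inpatient day. It is arithmetic that this scale rises by 1/(1 − f) when LOS falls by f. Whether the analysis would be affected depends on that scale being used and on LOS actually falling.

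If both happen, the distortion for assumed LOS cuts of 5% to 15% is about 5% to 18% in an affected unit and 4% to 12% pooled, given the assumed 70% share of days. The chance of a significant apparent increase would then be about 5% to 19% in a two-period comparison and 4% to 12% with silent controls, against 2.5%. It is lower with clustering or fewer non-ICU deaths, and higher with more deaths. These are illustrations, not this trial's operating characteristics.

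The plan's claim of 80% power for a relative difference below 1% is a separate error (187.5 deaths per period detect about 27%), and changing the scale does not repair it. The change should be made, and made before analysis.

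**What to change.** Before analysis:

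1. Define primary mortality as death before discharge per admission, analysed with a logit-link mixed model.
2. In the unit-level time series, use admissions as the denominator or offset, with a stated rule for attributing transferred patients and their deaths to units.
3. Restate the planning rate and the power on that scale, from admissions in the study units.
4. Report deaths per inpatient day as a secondary summary.
5. State as a limitation that deaths after an earlier discharge are missed, which could favour the intervention. Add death within a fixed window from admission as a sensitivity analysis if vital status is already available; the documents do not mention such data.

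**Cost.** SAP wording and modest programming on the same EHR data, with essentially no loss of power. Unit admission counts were known at planning. The real work is the transfer rule and the restated planning rate, because Table 1 has no admissions.
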